2.1.1.3 Demographics and other baseline characteristics

Smoking status

- **Smoker**: a subject is defined as smoker if “Has the subject ever smoked”= “Yes” and “Usage” = “Current”.
- **Non-Smoker**: a subject is defined as non-smoker if “Has the subject ever smoked”= “No” OR “Has the subject ever smoked”= “Yes” and “Usage” = “Former”.

TED history

- “Time (years) between onset of TED symptoms and Baseline” will be calculated as the difference between date of Baseline visit and date of onset of TED symptoms.
- “Time (years) between first diagnosis of TED and Baseline” will be calculated as the difference between date of Baseline visit and date of first diagnosis of TED.

Prior or concomitant medications (including previous TED treatments)

- Prior or concomitant medications will be grouped into categories “ophthalmic medications” and “non-ophthalmic medications”. Non-ophthalmic medications are those with “laterality” = “not applicable”.

2.1.1.4 Efficacy endpoints

Graves'orbitopathy – Quality of life questionnaire (GO-QoL)

The GO-Quality of life questionnaire (GO-QoL) comprises 2 subscales assessed separately. These 2 subscales are as follows:

- The consequences of double vision (diplopia) and decreased visual acuity on visual functioning and
- The psychological consequences of a changed appearance.

Total scores on each subscale will be calculated in the eCRF. Scoring rules used in the eCRF are defined in Appendix C ([Section 5.7](#)).

For other efficacy endpoints no specific definition is needed.

2.1.1.5 Safety endpoints

Discontinuation of treatment due to AE

Discontinuation of treatment due to AE is determined by the information given on the Adverse events eCRF page (action taken=“Drug withdrawn”). “Death” as a reason for treatment discontinuation will be summarized separately.

Treatment-emergent adverse events (TEAEs)

Treatment-emergent adverse events (TEAEs) are defined as adverse events (AEs) that occurred on or after the first dose of study treatment up to 84 days following the last dose of study treatment. In addition, AEs registered prior to start of double-blind treatment are considered as treatment-emergent if they have increased severity based on preferred term any time after the first dose of study treatment.

Serious adverse events (SAEs)

SAEs are determined by the flag on the Adverse Events eCRF page.

Treatment-related adverse event

Treatment-emergent adverse event is defined as treatment-related, if the investigator considered it as having a reasonable possibility to be related to study treatment, which is reflected in the eCRF with a corresponding flag.

Duration of exposure to AIN457 or Placebo (DBTP)

For calculations of exposure duration, last/ first dose date refers to receiving dose (prefilled syringe) > 0.

The duration of exposure to study treatment or placebo is computed as:

For patients completing the DBTP:

- Week 16 visit date – first dose date + 1.

For patients who discontinue treatment during DBTP:

- min (last dose date +84 days, Week 16 visit date) – first dose date + 1.

Duration of exposure to AIN457 (during entire study period)

For calculations of exposure duration, last/ first dose date refers to receiving dose (prefilled syringe) > 0. Duration of exposure will be defined as the time from first dose of study treatment to the time of treatment switch (for subjects who switch treatment) or minimum of (last dose of the treatment + 84 days) and (last visit date). Patients who switch treatment during the study (e.g., from placebo to active treatment) will have exposure to both medications using the appropriate start and stop dates (full details are described in Section 3.1 of the protocol [i.e. study protocol v01 dated 24-Aug-2021]).

2.2 Analysis sets

Mis-randomized patients who never received any study drug are considered as screen failures and are not included in the analysis sets.

Efficacy analysis

- The **Full analysis set (FAS)** will consist of all patients to whom study treatment (AIN457 or placebo) has been assigned. Following the intent-to-treat principle, patients will be analyzed according to the treatment they have been assigned to.

Safety analysis

The **Safety analysis set (SAF)** will consist of all patients who received at least one dose of study treatment during the treatment period. Patients will be analyzed according to the study treatment received.

Table 2-3 Treatment groups for safety analysis

Analysis period	Treatment group label
DBTP (up to Week 16)	AIN457 Placebo
Entire study period	AIN457 ¹ Placebo ² Any AIN457 ³

1 All patients randomized to secukinumab: This includes responders who receive no treatment after Week 16 and secukinumab non-responders or relapsers who go on open-label secukinumab.

2 Patients randomized to placebo with no open-label treatment in follow-up period. Any AEs reported in placebo patients prior to switching to AIN457 are also counted in this group.

3 Any AIN457 does not refer solely to just patients randomized to AIN457. It includes all patients who received at least one dose of secukinumab in DBTP or open-label follow-up. AEs occurring in placebo patients after switching to AIN457 are counted in this group.

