2.8.1 Adverse events (AEs)

In the frame of safety analysis the following treatment-emergent AE types will be considered:

- Any AE
- Study treatment related AE
- AE leading to study treatment discontinuation
- Serious AE (SAE)
- Study treatment related SAE
- SAE leading to study treatment discontinuation
- Death

- RMP risks

All AE tables will be summarized by treatment group.

The Medical Dictionary for Regulatory Activities (MedDRA) version 24.0 or later will be used to code all AEs to a system organ class (SOC) and a preferred term (PT).

An overview table of the number and percentage of patients having each type of AE will be given. Crude incidence and exposure adjusted incidence rates will be provided (see [Section 5.4.3](#) [safety analysis]).

Tables with number and percentage of patients having particular AE summarized by treatment group, SOC and PT will be provided for all AEs listed above except for death. Summaries will be provided for each AE type separately.

For AE type ‘any AE’ tables with number and percentage of patients having particular AE summarized by treatment group, SOC, PT and maximum severity will be provided.

The SOCs will be presented in the alphabetic order and PTs will be ordered within the SOCs by decreasing order of frequency in the secukinumab treatment group.

If a patient reported more than one AE with the same PT, the AE with the greatest severity will be presented. If a patient reported more than one AE within the same primary system organ class, the patient will be counted only once with the greatest severity at the system organ class level, where applicable.

All AEs, deaths, SAEs and AEs leading to permanent treatment discontinuation and leading to study discontinuation and AEs related to COVID-19 will be listed separately. In addition an ocular AE listing with laterality will be provided.

Table 2-4 Overview of analyses on some safety endpoints

Analysis period	AEs & SAEs	AEs by maximum severity	Study treatment related AEs	Notables for vitals, lab criteria
Day 1 – Week 16	•Crude incidence	•Crude incidence	•Crude incidence	•Crude incidence
Entire study phase	•Crude incidence Exposure time adjusted incidence	•Crude incidence	•Crude incidence	•Crude incidence

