5.4.3 Safety analysis

Crude incidence and $100*(1-\alpha)\%$ confidence interval

For n subjects, each at risk to experience a certain event with probability π , the crude incidence is estimated as $p=x/n$, where x is the number of subjects with the event.

Absolute and relative frequencies will be displayed as well as 95% CI for the relative frequency based on the score method including continuity correction ([Newcombe 1998](#)).

With z as $(1-\alpha/2)$ -quantile of the standard normal distribution (SAS: $z=PROBIT(1-\alpha/2)$), n as total number of subjects (i.e., number of subjects in the denominator), and p as estimated crude incidence (number of subjects with event / n) it is $q=1-p$.

Then the lower limit is:

$$L = \max(0, \frac{2np + z^2 - 1 - z\sqrt{z^2 - 2 - 1/n + 4p(nq + 1)}}{2(n + z^2)})$$

And the upper limit is:

$$U = \min \left(1, \frac{2np + z^2 + 1 + z \sqrt{z^2 + 2 - 1/n + 4p(nq + 1)}}{2(n + z^2)} \right)$$

Note: if $p < L$ then $L = p$ and if $p > U$ then $U = p$.

Exposure adjusted incidence rate and 100*(1- α)% confidence interval

It will be assumed that for each of n subjects in a clinical trial the time t_j ($j=1, \dots, n$) to the first occurrence of a certain treatment emergent event is observed, or if the event was not experienced, the (censored) time to the end of the observation period or last dose plus 84 days whichever occur earlier. The sequence of first occurrence of an event will be modelled to follow approximately a Poisson process with constant intensity Θ . The parameter Θ will be estimated as $\lambda = D/T$, where T is the sum of t_1 to t_n and D is the number of subjects with at least one event.

Conditionally on T , an exact 100* $(1-\alpha)\%$ CI for a Poisson variable with parameter ΘT and observed value D can be obtained based on [Garwood 1936](#) from which an exact 100* $(1-\alpha)\%$ CI for D/T will be derived as follows ([Sahai 1993](#); [Ulm 1990](#)):

Lower confidence limit $L = \frac{0.5c_{\alpha/2,2D}}{T}$ for $D > 0$, 0 otherwise,

Upper confidence limit $U = \frac{0.5c_{1-\alpha/2,2D+2}}{T}$

where $c_{\alpha k}$ is the α th quantile of the Chi-square distribution with k degrees of freedom.

Table 5-1 Examples for calculating exposure time for incidence rates (IR)

1st treatment / total exposure time	2nd treatment / total exposure time	AE event onset (in days from study start)	Exposure for IR
Placebo / 100 days	AIN457 / 200 days	Day 50 (during 1st treatment)	Placebo: 50 days

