		Day 110 (10 days into 2nd treatment)	AIN457: 10 days Any AIN: 10 days

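### Entire-study safety tables: the Placebo column counts switchers' events but not the switchers, and Table 5-1 credits a placebo switcher to AIN457

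*SAP*

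**What the plan says.** SAP 2.2, Table 2-3, defines three columns for the entire study period.

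- AIN457 (footnote 1): "All patients randomized to secukinumab: This includes responders who receive no treatment after Week 16", together with secukinumab non-responders and relapsers who go on to open-label drug.
- Placebo (footnote 2): "Patients randomized to placebo with no open-label treatment in follow-up period". The next sentence reads: "Any AEs reported in placebo patients prior to switching to AIN457 are also counted in this group".
- Any AIN457 (footnote 3): everyone with at least one secukinumab dose. For placebo patients who switch, "AEs occurring in placebo patients after switching to AIN457 are counted in this group".

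SAP 5.4.3 introduces crude incidence with "For n subjects, each at risk to experience a certain event with probability" π and estimates it as p = x/n, with a continuity-corrected score interval. The exposure-adjusted rate is D/T.

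SAP 2.1.1.5 says that patients who change treatment "will have exposure to both medications using the appropriate start and stop dates". Table 5-1 works an example with 100 days on placebo followed by 200 days on AIN457. An event on Day 50 counts 50 placebo days. An event on Day 110 counts "AIN457: 10 days Any AIN: 10 days".

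On the AE overview, SAP 2.8.1 states: "Crude incidence and exposure adjusted incidence rates will be provided". Table 2-4 shows that the entire study phase gets both measures for AEs and SAEs.

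**The concern.** There are two separate faults, both confined to the entire-study tables.

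(a) Footnote 2 leaves switchers out of the Placebo group but brings their pre-switch events in. Nothing in 5.4.3 adds them to n. A binomial proportion requires x to be a subset of n, so the literal rule overstates placebo crude incidence whenever a switcher had an AE before switching. The exposure-adjusted placebo rate does not share the fault, because switchers' placebo time and placebo events both enter it. Two measures printed in one Placebo column would then describe different sets of patients.

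(b) The Table 5-1 patient was randomized to placebo. Footnote 1 keeps that patient out of AIN457, and footnote 3 gives the post-switch event a home in Any AIN457. The Any AIN entry is therefore right and the AIN457 entry is not. If the example governs time and the footnotes govern events, switchers' person-time dilutes the AIN457 rates. If the example governs both, AIN457 and Any AIN457 become the same set, and the column for patients randomized to secukinumab disappears.

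Switching was probably common. SAP 1.2 reports no responders, SAP 1 reports that 23 of 28 randomized patients entered follow-up, and SAP 2.1.1 lists only sequences that move to open-label secukinumab.

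**Working it through.** **The plan's own figures.** The day counts in Table 5-1 reproduce: an event on Day 50 gives 50 days, and 110 − 100 = 10 days. The arithmetic is sound; the fault is the column to which the 10 days are credited.

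**Inputs.** From SAP 1: 28 randomized, 25 completed double-blind treatment, 23 entered follow-up. From SAP 2.1.1: 1:1 allocation. The documents do not give the arm split, the number of switchers, AE counts or follow-up lengths. I assume 14 patients per arm and show ranges for the rest.

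**(a) Placebo crude incidence.** Let k be the number of placebo patients who never switched and x the number of placebo patients with an AE before any switch. The literal rule gives x/k; with all placebo patients in n it is x/14. In principle k runs from 0 to 14. If everyone who entered follow-up took open-label drug, k is at most 28 − 23 = 5.

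| k | x = 6 (correct 6/14 = 43%) | x = 3 (correct 3/14 = 21%) |
|---|---|---|
| 14 | 43% | 21% |
| 10 | 60% | 30% |
| 7 | 86% | 43% |
| 5 | 120% | 60% |
| 3 | 200% | 100% |
| 2 | 300% | 150% |

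At k = 0 the proportion is undefined. It passes 100% from x = k + 1.

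The lower confidence limit in 5.4.3 takes the square root of z² − 2 − 1/n + 4p(nq + 1), with n = k, p = x/k and q = 1 − p. Since nq + 1 = k − x + 1:

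- x = 6, k = 5: 3.84 − 2 − 0.20 + 4(1.2)(0) = 1.6, so the limit can be computed.
- x = 6, k = 3: 3.84 − 2 − 0.33 + 4(2)(−2) = −14.5, so it cannot.

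For k = 1 to 12 the term is negative from x = k + 2 onwards.

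**(b) AIN457 person-time.** Let s be the number of placebo switchers, V the post-switch weeks each contributes, and W the weeks per patient randomized to secukinumab. The switchers' share of AIN457 time is sV/(14W + sV). Under the last-dose-plus-84-days rule, the last open-label dose at Week 28 gives maxima of W = 28 + 12 = 40 and V = 40 − 16 = 24.

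| W, V (weeks) | s = 6 | s = 11 |
|---|---|---|
| 24, 4 | 24/360 = 7% | 44/380 = 12% |
| 28, 12 | 72/464 = 16% | 132/524 = 25% |
| 40, 24 | 144/704 = 21% | 264/824 = 32% |

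With s = 0 the share is 0%. If time is added without events, D/T falls by exactly the share.

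If Table 5-1 is followed for events as well, the rate can move either way. Take 14 secukinumab patients at 250 days with 7 events, and 11 switchers at 150 days with 5 events (all assumed). Under footnote 1, AIN457 is 7/(3,500/365.25) = 73.1 per 100 patient-years. Under Table 5-1 it is 12/(5,150/365.25) = 85.1, identical to Any AIN457.

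**The case against.** The strongest reply is that a sensible reading exists. Section 2.1.1.5, the 50 placebo days in Table 5-1 and the at-risk premise of 5.4.3 all point to every placebo patient being counted up to the switch. SAP 2.1 leaves treatment-arm handling to the TFL shells, which are not available here and may already set n correctly. That is probably the intention, but the first sentence of footnote 2 says the opposite, and the shells would not remove the conflict between Table 5-1 and footnote 1.

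It is also fair that:

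- Percentages above 100 and uncomputable limits would be noticed. The risk lies in smaller inflation, such as 43% shown as 60%.
- The Week 16 table largely supplies the correct placebo figure. With no responders there are no relapsers, so pre-switch events are essentially double-blind events, and SAP 2.8 treats that period as the unbiased comparison.
- The direct conflict in (b) is with footnote 1. Table 5-1's Any AIN entry agrees with footnote 3, which bears on the point only by showing where the event belongs.
- The 7% to 32% dilution requires time and events to follow different rules, and it uses full exposure where 5.4.3 stops the clock at the first event. Under a constant hazard, that truncation shortens the longer secukinumab follow-up proportionally more, so the switchers' share would rise, not fall.
- All analyses are descriptive and no test depends on these columns.

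These points limit the consequences; they do not reconcile the text. This SAP was amended for the early termination, and the safety intervals in 5.4.3 are the only confidence-interval methods it specifies.

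**Conclusion.** Both contradictions hold on the wording alone, whatever the counts. Followed literally, footnote 2 inflates entire-study placebo crude incidence by the factor 14/k under an assumed arm of 14: none if nobody switched, 1.4 at k = 10, 2.8 at k = 5. Table 5-1 either dilutes the AIN457 exposure-adjusted AE and SAE rates (7% to 32% in the scenarios with 6 or 11 switchers) or makes that column a duplicate of Any AIN457.

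Confidence is high that the text is wrong as written. Whether wrong figures would be printed depends on the shells. The Week 16 tables are unaffected. The SAP should be corrected, but no efficacy conclusion depends on it.

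**What to change.** - **Table 2-3, footnote 2.** Define entire-study Placebo as all safety-set patients who received placebo. Count events and time from the first placebo dose to the earliest of first open-label dose, last placebo dose plus 84 days, or end of observation. State that the same patients supply x, n and T.
- **Table 5-1.** In the Day 110 row, delete the AIN457 entry and keep the 10 days under Any AIN. Leave the 50 placebo days of the Day 50 row unchanged.
- **TFL shells.** Confirm that the entire-study column counts use the same n.

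The cost is SAP and table-specification wording only. No new data are needed.

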2.2.1 Subgroup of interest

No subgroup analyses are planned.

2.3 Patient disposition, demographics and other baseline characteristics

2.3.1 Patient disposition

Randomized

Subjects are considered randomized if they have been assigned a randomization number.

Mis-randomized

Subjects are considered as randomized in error (=mis-randomized) if they were mistakenly randomized into the IRT prior to the site confirming all eligibility criteria had been met and to whom no study medication was given. Mis-randomized subjects will be treated as Screen Failures.

Screen failures

Subjects are considered as screen failure if they do not meet one or more criteria that were required for participation in the study.

Completing the DBTP

Subjects are defined as completing the DBTP if they complete all visits including Week 16 assessments. Subjects are defined as DBTP discontinuers if the Subject Status is not ticked as "Completed" for the blinded treatment disposition or if they missed any visit.

Completing the study

Subjects are defined as completing the study if they complete all visits including the follow-up visit (EOS). It will be derived from Study Disposition Form.

Patient disposition for the DBTP and follow-up period will be presented based on the FAS.

A corresponding summary will include number and percentage of patients (treatment group specific and overall). The primary reason for premature study discontinuation will be displayed by randomized treatment and overall.

The total number of patients screened and the number of screen failures will be summarized. The number of patients within each of the analysis sets used in the study will be given.

Protocol deviations (PDs) will be summarized separately for PDs not related to coronavirus 2019 (COVID-19) and for PDs related to COVID-19. For PDs not related to COVID-19, the number of patients with at least one PD will be presented (based on FAS) and the results of the PDs will be grouped using the broad categories (Selection criteria not met (Study eligibility); Withdrawal criteria met, but subject not withdrawn; Treatment deviation; Prohibited Concomitant Medication; Other). For PDs related to COVID-19, the number of patients with at least one PD will be presented (based on FAS) and the results of the PDs will be grouped by category of COVID-19 PD and type of relationship to COVID-19.

A complete list of the PDs can be found in the Edit Check Specifications document in the Clinical Regulatory Documentation and Information System (CREDI).

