### Glossary of terms

Premature patient withdrawal	Point/time when the patient exits from the study prior to the planned completion of all study drug administration and/or assessments; at this time all study drug administration is discontinued and no further assessments are planned
Randomization number	A unique identifier assigned to each randomized patient
Screen failure	A patient who did not meet one or more criteria that were required for participation in the study
Source data/Document	Source data refers to the initial record, document, or primary location from where data comes. The data source can be a database, a dataset, a spreadsheet or even hard-coded data, such as paper or electronic source (eSource)
Start of the clinical trial	The start of the clinical trial is defined as the signature of the informed consent by the first patient.
Study treatment	Any drug or combination of drugs or intervention administered to the study patients as part of the required study procedures; includes investigational drug(s), control(s) or background therapy
Study treatment discontinuation	When the patient permanently stops taking any of the study drug(s) prior to the defined study treatment completion date (if any) for any reason; may or may not also be the point/time of study discontinuation
Treatment arm/group	A treatment arm/group defines the dose and regimen or the combination, and may consist of 1 or more cohorts.
Variable (or endpoint)	The variable (or endpoint) to be obtained for each patient that is required to address the clinical question. The specification of the variable might include whether the patient experiences an intercurrent event.
Withdrawal of study consent (WoC)	Withdrawal of consent from the study occurs only when a patient does not want to participate in the study any longer and does not allow any further collection of personal data

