### Table 8-1 Assessment schedule (double-blind treatment period and follow-up for responders at Week 16)

### Novartis Amended Protocol (Version No. 02Track Changes)

### Page 55 of 99 Protocol No. CAIN457ADE16

Period	Screening Period		Treatment Period Post-Treatment Follow-Up 													
Visit Name	Screening (Week -6 to Baseline)	Baseline	Week 1	Week 2	Week 3	Week 4	Week 8	Week 12	Week 16	Week 20	Week 24	Week 32	Week 40	Week 56	Week 68	USV 
Days	-42 to -1	1	8	15	22	29	57	85	113	141	169	225	281	393	477	
Thyroid laboratory test (fasting)	х	х				х	х	х	х	х	х	х	х	х	х	(X)
QuantiFERON TB-PLUS test	x															
Serum pregnancy test	Х															
Urine pregnancy test (local analysis)		S				s	s	S	S	S	S	S	S		S	(S)
Adverse events (including injections site reactions)	Х	Х	Х	Х	Х	Х	Х	х	Х	Х	х	Х	Х	Х	х	Х
						i	i				i.					
Responder/NR-assessment									Х							
Prior/concomitant medications/non-drug therapy							Updat	te as neo	cessary							
CAS	Х	Х		Х		х	Х	Х	х	х	Х	Х	Х	х	Х	(X)
Proptosis measurement	Х	Х		Х		Х	Х	Х	Х	Х	Х	Х	Х	Х	Х	(X)
Diplopia grading 	Х	Х		Х		Х	Х	Х	Х	Х	Х	Х	Х	Х	Х	(X)
GO-QoL		Х		Х		Х	Х	Х	Х	Х	Х	х	х	Х	х	
Contact Interactive Response Technology (IRT)	x	Х	Х	Х	х	Х	х	х	х							

Confidential

Novartis	
Amended Protocol (Version No. 02Track Changes)	

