2.1.1.2 Visit and analysis window

Since the actual visit for a subject may not exactly coincide with their targeted visit date, the actual visit date is mapped to a study visit.

The nearest study day window will be utilized to define study visit for laboratory, vital signs, number of doses received, ophthalmological assessments and GO-QoL collected during office visits before dose is administered.

In case of multiple assessments within an analysis window, the day the closest to the scheduled visit day will be used.

Unscheduled visits will only be used when there is no measurement from the scheduled visit in the defined window. In case of multiple assessment values among the same type of visit (i.e., scheduled vs. unscheduled) within the same analysis window, the closest to the scheduled visit

day will be used. In case of equal distances (e.g., same day), the latest assessment value will be used.

For assessments that are not scheduled at all visits (e.g. hematology assessments) the derivation formula is:

- Lower limit = upper limit of previous visit +1.
- Upper limit = integer value of (target day + target day of next visit)/2.

Table 2-1 Study visit windows during DBTP

Study visit	Target day	Study day
DBTP		
Baseline	1	≤1
Week 1	8	2 – 11
Week 2	15	12 – 18
Week 3	22	19 – 25
Week 4	29	26 – 43
Week 8	57	44 – 71
Week 12	85	72 – 99
Week 16	113	100 – 127

Table 2-2 Study visit windows during open-label treatment and follow-up for non-responders

Study visit	Target day	Study day
Week NR 16*	113	100 – 116
Week NR 17	120	117 – 123
Week NR 18	127	124 – 130
Week NR 19	134	131 – 137
Week NR 20	141	138 – 155
Week NR 24	169	156 – 183
Week NR 28	197	184 – 211
Week NR 32	225	212 – 253
Week NR 40	281	254 – 337
Week NR 56	393	338 – 448

*Only applicable for assessments that have not been performed at Week 16 visit in non-responders.

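### SAP 2.3.1 makes any missed visit a double-blind-period discontinuation, even when the disposition form says Completed and Week 16 was assessed

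*SAP*

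**What the plan says.** SAP 2.3.1 gives two linked definitions for the DBTP. A completer has attended every visit and has the Week 16 assessments. A discontinuer is a patient whose subject status is other than Completed "for the blinded treatment disposition or if they missed any visit". The two conditions are joined by 'or', so either is sufficient. The result is tabulated on the FAS: "A corresponding summary will include number and percentage of patients (treatment group specific and overall").

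Other places bear on the same patients:

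- Protocol section 8, before the assessment tables, says that a visit that is missed or moved is not to bring about discontinuation automatically.
- The protocol glossary defines study treatment discontinuation as "When the patient permanently stops taking any of the study drug(s) prior to the defined study treatment completion date".
- Protocol section 6.5 foresees, in limited circumstances, a temporary interruption of study treatment followed by a restart.
- SAP 2.1.1.5 computes DBTP exposure in two branches only: "For patients completing the DBTP" and "For patients who discontinue treatment during DBTP".
- SAP section 1 reports 28 patients randomized and 25 who completed the DBTP, without saying how completion was judged.

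**The concern.** The missed-visit clause overrides the disposition form. A patient who skipped one visit, came back, finished dosing and was assessed at Week 16 would be tabulated with patients who stopped treatment or left. A reader of the disposition table takes a discontinuation count as a measure of tolerability and of how complete the blinded comparison was. Under this rule the count also contains visit adherence, and the two cannot be separated. The table could also disagree with the disposition form and with the figure of 25 completers in SAP section 1, with nothing in the plan to explain the difference.

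**Working it through.** The plan states no DBTP discontinuation rate, so there is no figure of its own to reproduce. The check has three parts.

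**1. One patient followed through the rules.** Take a patient who misses a single visit between Baseline and Week 16 (Week 1, 2, 3, 4, 8 or 12), resumes, has Week 16 assessed, and has status Completed on the form.

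| Rule | Result for this patient |
|---|---|
| SAP 2.3.1, completer | No: not every visit attended |
| SAP 2.3.1, discontinuer | Yes: one missed visit is enough |
| Protocol section 8 | Not automatically discontinued |
| Protocol glossary | Has not discontinued treatment: no permanent stop |
| SAP 2.1.1.5, completing branch | Not met, because not a completer under 2.3.1 |
| SAP 2.1.1.5, discontinuing branch | Not met, because treatment was not discontinued |

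Neither document exempts this patient from the missed-visit clause.

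**2. Size in the disposition table.** Inputs: 28 randomized (SAP sections 1 and 3); FAS = all patients assigned treatment, less mis-randomized patients who were never dosed (SAP 2.2); allocation 1:1 (SAP 2.1.1). Each reclassified patient changes the rate by 100 × 1/N points.

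- Overall, N = 28: 100/28 = 3.6 points. If one or two patients were excluded as mis-randomized: 100/27 = 3.7 or 100/26 = 3.8.
- By arm, sizes not given: 100/14 = 7.1 points if the split is even; 100/16 = 6.3 to 100/12 = 8.3 points for arms of 16 to 12.
- Illustration, assuming that the 25 were counted by form status and that the other 28 − 25 = 3 are all discontinuers: 3/28 = 10.7%. With one, two or three reclassified patients: 4/28 = 14.3%, 5/28 = 17.9%, 6/28 = 21.4%.

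**3. Size in the exposure summary.** The completing branch gives Week 16 date − first dose date + 1. The discontinuing branch replaces the Week 16 date by the earlier of that date and last dose + 84 days. The windows come from SAP Table 2-1, "Study visit windows during DBTP": Week 4 is Days 26–43, Week 8 is Days 44–71 and Week 16 is Days 100–127.

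- Last dose in or after the Week 8 window: at the earliest, Day 44 + 84 = Day 128, which is later than Day 127. The minimum is then always the Week 16 date, and the two branches agree.
- Weeks 8 and 12 both missed, Week 4 dose and Week 16 visit on target: 29 + 84 = 113, the Week 16 target day, so there is again no difference.
- The same case with the earliest Week 4 day and the latest Week 16 day: 26 + 84 = 110, and 127 − 110 = 17 days' difference.

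Exposure can therefore differ only for a patient who missed several doses, and then usually by little.

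**The case against.** The best defence is that 2.3.1 defines completion of a period, whereas the glossary defines discontinuation of treatment, and that the two halves of 2.3.1 agree with each other. On this view it is a strict but open convention, and the sentence in protocol section 8 is about keeping patients in the trial, not about tabulation. Part of this stands: a strict per-visit completer category would be legitimate under its own name. But the SAP calls these patients discontinuers and ranks a missed visit above a form status of Completed. It then uses completing and discontinuing treatment as the only two exposure categories. The conflict therefore remains.

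Four stronger readings are tempting, and the documents do not support them.

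- A reader might infer that missing Week 1 or Week 3 is harmless because Table 8-1 schedules no CAS or proptosis measurement there. The same table schedules study drug, vital signs and adverse event review at both visits. A missed visit there will usually mean a missed dose, which deserves reporting, though not as a discontinuation.
- A reader might infer that the study-completion definition has the same fault, since it reads "Subjects are defined as completing the study if they complete all visits including the follow-up visit (EOS"). That definition has no missed-visit clause for discontinuers, and the SAP goes on to derive the status from the Study Disposition Form. Only the wording about all visits is loose.
- A reader might see a contradiction in one patient being both a DBTP discontinuer and present in follow-up. Protocol 9.1.1 keeps patients who stop treatment in the study, with further visits, so this can occur by design.
- A reader might infer that the reported rate is already inflated. The documents give no count of missed visits, and 1/28 is simply the weight of any one patient.

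**Conclusion.** The rule is wrong as written, and the point is minor. It conflicts with protocol section 8 and with the glossary's permanent-stop definition, and it leaves a patient who misses a visit and resumes without an exposure branch. Each such patient, if there are any, adds 3.6 points to the overall DBTP discontinuation rate, assuming that all 28 are in the FAS, and about 7 points within an arm, assuming 14 per arm. The total may be zero.

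Only descriptive disposition is materially affected. Membership of the FAS and the safety set does not depend on completion status, efficacy is summarized on the FAS, and no superiority test is made. The table shells and the protocol deviation specifications are not among the documents, so a clarification there cannot be ruled out.

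**What to change.** - In SAP 2.3.1, delete the missed-visit alternative. Define DBTP completers as FAS patients with blinded-treatment disposition status Completed and a Week 16 assessment, and DBTP discontinuers as all other FAS patients.
- In SAP 2.1.1.5, assign the two DBTP exposure branches by that same status, so that every patient falls into exactly one.
- Report missed visits or doses, including missed Week 1 and Week 3 dosing visits, in the protocol deviation summary that 2.3.1 already plans.
- In the study-completion definition, drop only the phrase about all visits and leave the derivation from the Study Disposition Form as it is.
- In SAP section 1, state which definition the 25 completers follow.

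The cost is two or three sentences in 2.3.1 and one clause each in 2.1.1.5 and section 1. No new data are needed.
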